8.3.2.4. Grade 2 or Higher Non-diarrheal GI AEs

For CTCAE Grade 2 or higher non-diarrheal GI AEs (e.g., nausea, vomiting, abdominal pain) measures described in Section 8.3.2.1 for Grade 1 events should be considered, including anti-emetic medications for nausea and vomiting, if clinically appropriate. In addition, investigators should remain vigilant to worsening of symptoms over time and interrupt BCV if non-diarrheal GI AEs reach Grade 3 in intensity.

For one or more Grade 3 or higher non-diarrheal GI events, BCV dosing must be interrupted.

If non-diarrheal GI AE(s) improve to \leq Grade 2 in intensity, subjects who have interrupted BCV may resume dosing, but no sooner than 7 days (i.e., at least 6 full days off drug) following the last BCV dose administration.

- If resumed, BCV must be administered in a consolidated QW dose (total weekly dose administered once weekly, i.e., 4 mg/kg QW up to a maximum of 200 mg QW in the absence of concurrent cyclosporine or 2.8 mg/kg up to a maximum of 140 mg QW for

subjects taking concurrent cyclosporine) to potentially improve tolerability, as weekly dosing intervals allow more time for GI mucosal regeneration between doses.

If non-diarrheal GI AE(s) do not improve during interruption, BCV must not be resumed.

In the event of recurrence of CTCAE Grade 3 or higher non-diarrheal GI AEs after restarting BCV, BCV may be allowed to continue only after discussion and agreement with the Chimerix Medical Monitor (or designee).

8.3.2.5. Elevations in Serum Aminotransferases

Treatment with BCV must be interrupted for at least 7 days (i.e., at least 6 full days off drug) if any of the following confirmed abnormalities occur:

1. ALT or AST > 8x ULN and \geq 2x baseline value
2. ALT or AST > 5x ULN and \geq 2x baseline value for more than 2 weeks
3. ALT or AST > 3x ULN and \geq 2x baseline value **and** total bilirubin > 2x ULN **or** PT-INR > 1.5x ULN
4. ALT or AST > 3x ULN and \geq 2x baseline value with the appearance of fatigue, nausea, vomiting, right upper quadrant pain or tenderness, fever, rash, and/or eosinophilia (> 5%)
5. Total bilirubin > 3 mg/dL and \geq 2x baseline value

Abnormal laboratory values should be confirmed at the central laboratory as soon as feasible. Both initial and confirmatory values should be central laboratory values, however, if waiting for central laboratory confirmation is not deemed clinically appropriate, a sample can be drawn in parallel for local laboratory analysis, and if necessary, BCV may be interrupted pending further investigation of the laboratory abnormalities.

If confirmed, increases in serum aminotransferases, as described above, should result in immediate interruption of BCV dosing. The investigations to be undertaken should include, but are not limited to: imaging, testing for hepatotropic infections, evaluations for GVHD, review of other concomitant medication, and possibly liver biopsy, as appropriate. Potential lactic acidosis should also be ruled out. For subjects on azoles, interruption of dosing with azoles should be considered if criterion 2 above is the only one met (i.e., there is no bilirubin elevation).

If an alternate reason for the laboratory abnormalities is identified and after the abnormalities decrease by \geq 1 CTCAE grade below the grade that triggered BCV interruption listed above, dosing with BCV may resume, however, BCV should be administered as a consolidated weekly dose (i.e., 4 mg/kg, up to a maximum of 200 mg, QW in the absence of concurrent cyclosporine, or 2.8 mg/kg, up to a maximum of 140 mg, QW for subjects taking concurrent cyclosporine).

Generally, subjects with persistent and significant ALT or AST elevations (> 5x ULN) should not resume administration of BCV unless there is clear evidence of a causal association with a viral disease being treated. In these cases, continued treatment with BCV may be allowed after discussion and agreement with the Chimerix Medical Monitor (or designee).

Recurrence of the liver abnormalities after reintroduction of BCV requires permanent discontinuation of BCV.

8.3.2.6. Decrease in Estimated Glomerular Filtration Rate to < 15 mL/min

To be eligible for this study, subjects must have an estimated creatinine clearance of ≥ 30 mL/min and must not have received renal replacement therapy (e.g., hemodialysis, continuous renal replacement therapy, or peritoneal dialysis) within 7 days prior to Day 1. In cases where the eGFR of a subject receiving BCV therapy decreases to < 15 mL/min, the benefit:risk proposition of continuing treatment with BCV must be re-evaluated for the subject, because even with dialysis there remains a risk of increased CDV exposure. Given the lack of alternative therapy for treatment of AdV in the setting of end-stage renal disease, continuation of BCV in a subject receiving dialysis may be considered after consultation with the Chimerix Medical Monitor and/or designee.

8.4. Re-initiation of BCV Dosing for AdV Viremia

Subjects who stop BCV therapy due to confirmed undetectable AdV viremia may re-initiate treatment with BCV if AdV viremia is subsequently confirmed at ≥ 1000 copies/mL by the designated central virology laboratory. For the purposes of re-initiating BCV therapy, “confirmed viremia ≥ 1000 copies/mL” is defined as two consecutive results ≥ 1000 copies/mL from the designated central laboratory, with the second sample drawn at least 48 hours after the first sample. BCV dosing will be resumed at the same dose and dose frequency the subject was receiving when BCV therapy was stopped (e.g., if BCV dosing had been consolidated to QW administration for toxicity management purposes, the subject would resume at the QW dose). Subjects should be managed as per the toxicity monitoring and management criteria as outlined in Section 8.3.2.

Subjects who permanently discontinue BCV for toxicity reasons are not eligible to re-initiate BCV dosing.

8.5. Access to BCV after Week 16

Subjects randomized to the BCV arm may receive up to 16 weeks of therapy with BCV (through Week 16 post-randomization). Treatment with BCV may not be extended past Week 16 under this protocol. Therefore, investigators wishing to extend or re-initiate treatment with BCV for a subject after Week 16 will need to request access to the drug through the local NPP (or other expanded access program), where available. If applicable, approval for access to BCV through the NPP should be secured prior to the subject completing the Week 16 assessment to ensure continuity of care.

Subjects randomized to the SoC arm are not allowed to receive BCV during the 16-week treatment period, whether under this protocol or through an expanded access mechanism. After completion of the Week 16 assessment, investigators may request access to BCV through the local NPP (or other expanded access program), where available.

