- 2 mg/kg (up to a maximum of 100 mg) twice weekly (BIW) for subjects not receiving concurrent cyclosporine
- 1.4 mg/kg (up to a maximum of 70 mg) BIW for subjects receiving concurrent cyclosporine (i.e., subjects taking cyclosporine on Day 1 or who initiate cyclosporine at any time while taking BCV)

Subjects who discontinue cyclosporine while taking BCV should increase the BCV dose to 2 mg/kg (up to a maximum of 100 mg), starting with the next scheduled BCV dose following discontinuation of cyclosporine.

Each dose of BCV will be administered orally as an oral suspension of 10 mg/mL strength. The dose of BCV to be administered will be calculated using the lowest body weight recorded for the subject in the 30 days prior to Day 1. Whenever possible, the BCV doses should be given with food (with or within 30 minutes after finishing a meal) to potentially improve tolerability. Subjects who are unable to take medicines orally may be dosed through a nasogastric tube, gastrostomy tube, or other feeding tube that allows the dose to be delivered directly into the subject's stomach or duodenum.

Intrajejunal delivery is not advised as PK and tolerability data are not available for this route of administration. The BCV doses should be administered at alternating 3- and 4-day intervals unless dosing is modified for tolerability reasons, as described below.

Duration of Treatment/Study:

For subjects randomized to the BCV arm, BCV will be administered for a maximum of 16 weeks, based on virologic response to treatment and tolerance to the drug. In the absence of toxicity requiring dose interruption, BCV will be administered BIW until plasma AdV viremia is confirmed undetectable (two consecutive plasma viral load results of "undetectable" as reported by the designated central virology laboratory), or until Week 16 post-randomization, whichever occurs first. After a subject's first AdV plasma viral load result is reported as "undetectable" by the designated central virology laboratory, a confirmatory blood sample must be drawn no sooner than 7 days (6 full calendar days and no later than 14 days (13 full calendar days) after the first sample was drawn. Once AdV viremia is confirmed as undetectable, BCV will be discontinued.

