Until a subject has achieved sufficient immune reconstitution, reactivation of latent virus from the gut may result in a subsequent episode of AdV viremia. Subjects who stop BCV therapy after achieving confirmed undetectable AdV viremia may re-initiate treatment with BCV if AdV viremia is subsequently confirmed at ≥ 1000 copies/mL by the designated central virology laboratory, unless precluded by the BCV toxicity management guidelines. For the purposes of re-initiating BCV therapy, "confirmed AdV viremia ≥ 1000 copies/mL" is defined as two consecutive results ≥ 1000 copies/mL from the designated central laboratory, with the second sample drawn at least 48 hours after the first sample. BCV dosing will be resumed at the same dose and dose frequency the subject was receiving when BCV therapy was stopped (i.e., if BCV dosing had been consolidated to once weekly [QW] administration for toxicity management purposes, the subject would resume at the QW dose).

Subjects who permanently discontinue BCV for toxicity reasons are not eligible to re-initiate BCV therapy.

Treatment with BCV may not be extended past Week 16 under this protocol. Therefore, investigators wishing to extend or re-initiate treatment with BCV for a subject after Week 16 will need to request access to the drug through the local named patient program (NPP) or other expanded access program, where available.

The duration of any therapy administered as part of SoC will be determined by local institutional practice. Subjects randomized to the SoC arm will be managed according to local institutional practice and guidelines and any relevant product labelling. To allow for a meaningful and interpretable comparison of safety and efficacy between treatment arms, subjects randomized to the SoC arm will NOT be eligible to receive BCV therapy prior to Week 16 post-randomization. After completion of the Week 16 assessment, subjects randomized to the SoC arm may be able to access BCV through the local NPP or other expanded access program, as described above.

All subjects will be followed for a period of 36 weeks post-randomization, regardless of treatment assignment, including SoC subjects who begin BCV treatment after Week 16 post-randomization.

Reference Therapy, Dosage and Mode of Administration:

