4.3.3. Rationale for BCV Dosage Regimen and Treatment Duration

[figure not shown]
Subjects will receive a BCV dosage regimen based on their lowest body weight measurement within 30 days prior to Day 1 (to best represent dry weight) and concurrent cyclosporine use. Subjects not receiving concurrent cyclosporine will receive BCV at a dose of 2 mg/kg (up to a maximum of 100 mg) BIW. Subjects receiving concurrent cyclosporine will receive 1.4 mg/kg (up to a maximum of 70 mg) BIW; the BCV dose is adjusted to account for increased exposures observed with cyclosporine co-administration. See Section 8.2 for additional dosing details.

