6.4. Treatment Assignment

Subjects who meet all eligibility criteria will be randomized in a 2:1 ratio to BCV or SoC according to the randomization code through an automated interactive voice or web response system (IV/WRS).

- Arm 1: BCV until plasma AdV viremia is confirmed undetectable, up to a maximum of 16 weeks. BCV suspension will be dosed at 2 mg/kg, up to a maximum of 100 mg, BIW, or, for subjects taking concurrent cyclosporine, at 1.4 mg/kg, up to a maximum of 70 mg. Details of the dosing algorithm are in Section 8.3.
- Arm 2: Local or institutional SoC.

BCV and any SoC regimens will be administered open-label. The first dose of BCV should be administered as soon as possible following randomization and must be administered no more than 24 hours after randomization.

All subjects, regardless of treatment assignment, will be followed for a period of 36 weeks post-randomization.

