8.2. BCV Administration

Subjects randomized to the BCV treatment arm will receive BCV administered orally as 10 mg/mL suspension.

Subjects will receive a BCV dosage regimen based on their lowest body weight within 30 days prior to Day 1 (to best represent dry weight) and their concurrent cyclosporine use (Table 6).

Table 6: BCV Dosage Regimens for Study CMX001-999

	Initial BCV Dose Regimen	Consolidated BCV Dose Regimen
Cyclosporine	1.4 mg/kg (up to maximum 70 mg) BIW	2.8 mg/kg (up to maximum 140 mg) QW
No cyclosporine	2 mg/kg (up to maximum 100 mg) BIW	4 mg/kg (up to maximum 200 mg) QW

Note: Dosing weight = lowest body weight (in kilograms) within 30 days prior to Day 1.

Abbreviations: BIW = twice weekly; QW = once weekly

As described in Section 8.6, co-administration of BCV and cyclosporine has been shown to increase plasma BCV exposure. Therefore, subjects taking cyclosporine on Day 1 or who initiate cyclosporine at any time while taking BCV will receive a modified dose of BCV of 1.4 mg/kg, up to a maximum of 70 mg, BIW. Subjects who discontinue cyclosporine while taking BCV should increase the BCV dose to 2 mg/kg, up to a maximum of 100 mg, starting with the next scheduled BCV dose following the discontinuation of cyclosporine.

Each BCV dose should be administered using an oral dosing syringe. A 5-mL dosing syringe is recommended for BCV doses \leq 50 mg, and a 10-mL dosing syringe is recommended for BCV doses $>$ 50 mg. [Note: The study drug kits DO NOT include oral dosing syringes.]

Referring to Section 8.3.2, subjects who resume BCV therapy after a mandated interruption due to a TEAE will resume therapy at a consolidated QW dose of 4 mg/kg (up to a maximum of 200 mg) QW for subjects not receiving concurrent cyclosporine, or 2.8 mg/kg (up to a maximum of 140 mg) QW for subjects receiving concurrent cyclosporine (Table 6).

The dose (volume of BCV oral suspension to be administered) should be determined using the dosing tables provided in Appendix 2 (see Table 14 for BCV dosing of subjects receiving concurrent cyclosporine and Table 15 for BCV dosing of subjects not receiving concurrent cyclosporine).

See Section 9 for detailed description of appropriate storage and management of BCV.

Whenever possible, the BCV doses should be given with food (with or within 30 minutes of finishing a meal) to potentially improve tolerability.

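### Restarting brincidofovir at the same dose after relapse makes no allowance for cyclosporine started or stopped while off drug, and so conflicts with the cyclosporine-based doses in Table 6

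*Combined protocol and SAP*

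**What the plan says.** **Re-initiation rule.** A child who stopped brincidofovir (BCV) after confirmed clearance may restart if viremia of at least 1000 copies/mL is confirmed. On the dose, Section 8.4 says: "BCV dosing will be resumed at the same dose and dose frequency the subject was receiving when BCV therapy was stopped". The Synopsis (Duration of Treatment/Study) uses the same sentence. Both illustrate it only with dose consolidation. The Synopsis writes "i.e., if BCV dosing had been consolidated to once weekly [QW] administration for toxicity management purposes"; Section 8.4 writes "e.g., if BCV dosing had been consolidated to QW administration for toxicity management purposes". The only section that 8.4 points to for managing these children is 8.3.2, on toxicity.

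**Cyclosporine switch rules.** The Synopsis defines the reduced-dose group as "subjects taking cyclosporine on Day 1 or who initiate cyclosporine at any time while taking BCV". Section 8.2 is worded in the same way: those "who initiate cyclosporine at any time while taking BCV will receive a modified dose of BCV of 1.4 mg/kg". The matching rule for stopping cyclosporine is also limited to children who stop it during BCV treatment.

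**Status-based dosing.** Table 6 in Section 8.2 has one row for cyclosporine and one for no cyclosporine. Section 8.2 says the volume "should be determined using the dosing tables provided in Appendix 2", which has a separate table for each status. Section 4.3.3 says "Subjects receiving concurrent cyclosporine will receive 1.4 mg/kg (up to a maximum of 70 mg) BIW", and Section 6.4 gives the dose "for subjects taking concurrent cyclosporine, at 1.4 mg/kg, up to a maximum of 70 mg". Section 8.6 assigns the lower Table 6 dose to anyone on concurrent cyclosporine. The toxicity-resumption rules (Sections 8.3.2.2 to 8.3.2.5) each state both weekly doses, with and without cyclosporine.

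**The concern.** Cyclosporine status can change during the interval off BCV. A change then meets none of the conditions in the switch rules, so the only instruction addressed to the restart is to repeat the old dose. The Synopsis definition points the wrong way in both directions. A child who starts cyclosporine off drug falls outside it, and a child on cyclosporine at Day 1 who stops it off drug stays inside it.

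The case is foreseeable. The protocol expects recurrence while immunity is poor. Section 4.3.2 cites guidance to reduce immunosuppression where possible, and Section 8.6 asks sites to consider alternatives to cyclosporine.

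At stake is a dosing error at restart. With newly started cyclosporine, the literal rule gives unadjusted BCV. Section 8.6 associates that combination with higher odds of Grade 2 or higher bilirubin elevation and of more serious hepatobiliary events, and Section 4.3.3.1 names the dose reduction as a step to avoid high exposure. PK sampling is confined to Day 1 (or Day 4) and Week 2 (Section 10.4.1), so excess exposure at a later restart would not be measured. In the other direction the child is under-dosed. That is the lesser worry, since Section 4.3.3.1 says antiviral activity does not need high exposure.

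**Working it through.** **Inputs**
- Doses (Table 6): without cyclosporine, 2 mg/kg twice weekly (BIW, max 100 mg) or 4 mg/kg once weekly (QW, max 200 mg). With cyclosporine, 1.4 mg/kg BIW (max 70 mg) or 2.8 mg/kg QW (max 140 mg).
- Interaction in patients: steady-state AUC rises by about 43% (Section 8.6).
- Volumes: Table 14 (with cyclosporine) and Table 15 (without), at 10 mg/mL (Appendix 2).
- Between-subject spread: %CV of dose-normalized weekly AUC is 65 to 96 across the pediatric age groups (Table 3).

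**1. Reproduce the plan's adjustment.** Adjusted dose = unadjusted dose / 1.43, taking exposure as proportional to dose.
- BIW: 2 / 1.43 = 1.399, stated 1.4 mg/kg.
- QW: 4 / 1.43 = 2.797, stated 2.8 mg/kg.
- Caps: 100 / 1.43 = 69.9 and 200 / 1.43 = 139.9, stated 70 and 140 mg.

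The Table 6 doses therefore cancel the 43% interaction: 0.70 × 1.43 = 1.00.

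**2. Apply the two instructions to the same child.**

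| Change while off BCV | Section 8.4, literal | Table 6 | Ratio, literal / Table 6 |
|---|---|---|---|
| Cyclosporine started, BIW | 2 mg/kg | 1.4 mg/kg | 2 / 1.4 = 1.43 |
| Cyclosporine started, QW | 4 mg/kg | 2.8 mg/kg | 4 / 2.8 = 1.43 |
| Cyclosporine stopped, BIW | 1.4 mg/kg | 2 mg/kg | 1.4 / 2 = 0.70 |
| Cyclosporine stopped, QW | 2.8 mg/kg | 4 mg/kg | 2.8 / 4 = 0.70 |

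**3. Check against the rounded volumes.**
- 20 kg, BIW: 4 mL (40 mg) against 2.8 mL (28 mg). QW: 8 mL (80 mg) against 5.6 mL (56 mg).
- 48 kg and above, BIW: 10 mL (100 mg) against 7 mL (70 mg).
- From 5 to 48 kg, the smallest ratio is 4.5 / 3.4 = 1.32 at 23.7 kg and the largest is 1.1 / 0.7 = 1.57 at 5.3 kg. In reverse the range is 0.7 / 1.1 = 0.64 to 3.4 / 4.5 = 0.76.

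**4. Exposure, if proportional to dose.** Take 2 mg/kg without cyclosporine as 1.00.
- Cyclosporine started: literal dose 1.00 × 1.43 = 1.43; Table 6 dose 0.70 × 1.43 = 1.00.
- Cyclosporine stopped: literal dose 0.70; Table 6 dose 1.00.

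Section 4.2.2 reports more than proportional exposure in children after single doses from 2 to 4 mg/kg. The QW doses of 2.8 and 4 mg/kg lie in that range, so their exposure ratio may exceed 1.43. The healthy-volunteer interaction in Section 8.6 (4.74-fold) is not used, because the protocol bases its adjustment on the smaller effect in patients.

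**5. Who is affected.** A child must clear, stop BCV, relapse with two results of at least 1000 copies/mL, restart before Week 16, and change cyclosporine in the gap. The documents give no frequency for this sequence.

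**The case against.** **The right dose is stated elsewhere.** Section 8.6 is not limited to Day 1 or to changes during treatment. Section 8.2 sends the site to Appendix 2, which splits the tables by cyclosporine use and asks staff to verify the table. This stands in part: a careful site could reach the right dose, more easily when cyclosporine was started than when it was stopped. But it shows two instructions in conflict, and Section 8.4 is the one written for the restart.

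**The sentence may be meant to fix frequency only.** Its sole illustration is weekly consolidation, and the Synopsis introduces it with i.e., as though defining the rule. This reading is plausible. Against it, the sentence names dose and dose frequency separately, and Section 8.4 gives the same case only as an example.

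**The dosing flow chart may settle it.** Appendix 3 is a figure whose content is missing from the available text. It could not be checked, so the point is limited to the written sections.

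**The consequence is small.** This largely stands. Few children should be affected. A 1.43-fold shift lies within ordinary between-subject spread. Section 8.6 describes the BCV and cyclosporine effects as independent rather than synergistic and asks for close hepatobiliary monitoring. The liver interruption rules in Section 8.3.2.5 and the weekly chemistry in Table 5 still apply. These limits lower the priority but do not remove the contradiction.

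**Conclusion.** The concern holds on the literal reading. Section 8.4 and the Synopsis state a restart rule that departs from Table 6 whenever cyclosporine status changes while the child is off BCV. Two sites could give the same child different doses and each cite the protocol.

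The literal dose is nominally 1.43 times the intended one if cyclosporine was started (1.32 to 1.57 after rounding) and 0.70 times if it was stopped (0.64 to 0.76). The dose ratios follow directly from Table 6 and Appendix 2. The exposure figures also assume dose proportionality and the 43% interaction.

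Confidence is moderate, because the frequency-only reading is tenable and Appendix 3 was not visible. The wording should be corrected, since it can produce the wrong dose in a foreseeable case with a hepatobiliary safety link. It does not bear on the power, endpoints or primary analysis.

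**What to change.** In Section 8.4 and in the Synopsis (Duration of Treatment/Study), say that BCV is resumed at the same dose frequency, BIW or QW, at the Table 6 dose for the subject's cyclosporine status at re-initiation. Check that the Appendix 3 flow chart agrees.

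As an optional clarification, add the weekly doses to the start and stop sentences in Section 8.2 and the Synopsis, which now give only the twice-weekly ones: 2.8 mg/kg (max 140 mg) on starting cyclosporine and 4 mg/kg (max 200 mg) on stopping it. Table 6 already has these doses and needs no change.

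The cost is a one-phrase clarification by amendment or site memo, with no effect on sample size, endpoints or analysis.
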